63	improving their problem-solving abilities through caffeine.
~ ^	

Graham Marsden and John Leach also found that caffeine improved visual search performance in experienced navigators [21], which may also be related to emergency physicians' ability to search for lesions on diagnostic clues and medical images. In addition, caffeine has been shown to improve performance and cognitive functioning in shift workers in a review of the literature [24]. In recent years, caffeine chewing gum has been marketed to facilitate and accelerate caffeine intake [25], and studies have

70	examined the effects of caffeine gum on cognitive performance in e-sports players [17].
71	However, no studies have been conducted on the effects of caffeine supplementation on
72	cognitive functioning in night-shift emergency physicians with caffeinated chewing
73	gum.
74	This study aims to investigate whether caffeine supplementation with caffeinated
75	chewing gum can be used by emergency physicians during night shifts to maintain
76	proper cognitive functioning and thus patient safety. At the same time, sleep monitoring
77	was performed to observe whether caffeine supplementation affected subsequent sleep.
78	This is to provide emergency physicians with a reference for caffeine supplementation
79	with caffeine gum during night shift work.
80	
81	2. Methods
82	2.1. Design
83	This experiment was a double-blind, repeated-measures, crossover design
84	according to the guidelines of CONSORT 2010[26] and was divided into either a
85	caffeine trial (CAF) or a placebo trial (PL). To eliminate the impact of individual
86	physical differences, a crossover trial was conducted with the same group of subjects.
87	Randomized groups were created using Microsoft 365-Excel (Microsoft, Redmond,
88	Washington, United States), and allocation was randomized and unpredictable. Each

89	trial was separated by at least four weeks to avoid interactive effects. This study
90	compared CAF and PL trial to determine the effects of caffeinated chewing gum on
91	cognitive performance in emergency physicians engaged in night shift work., and
92	subjective, objective sleep quality. Caffeinated chewing gum and placebo chewing gum
93	are very similar in appearance, color, size, shape, and flavor and are difficult to
94	distinguish. The randomization was carried out by a research assistant, with another
95	resident performing the experiment, and neither the subjects themselves nor the resident

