96	experimenting knew which group the subjects were assigned to or what type of gum
97	they were assigned. Once the data has been collected, it will be forwarded to the group's
98	statistical analyst for statistical analysis, who was also unaware of the group
99	assignments. At least one week before the formal experiment, all subjects participated
100	in three to five familiarization tests for the cognitive function tests. Sleep quality was
101	also assessed subjectively by a single question score, and objectively by ActiGraph for
102	one night on the off day and the last sleep before the first night shift. The primary
103	outcome was the results of cognitive function tests, and the secondary outcome was the
104	sleep quality.

106 2.2. Participants

107 Fourteen healthy male emergency physicians were recruited in this study and

based on previous research on caffeine in e-sport athletes [17, 18], we used the G*power 108 3.1 software 24 to achieve an alpha value of 5% and a power of 0.8, which was 109 110 sufficient for the study with only six subjects. However, due to the lack of relevant studies on the effects of caffeine and caffeinated chewing gum on cognitive functioning 111 in night-shift healthcare workers, reference was made to a recent study that examined 112 the cognitive performance of emergency physicians after 24 consecutive hours of on-113 call duty, which included 13 subjects [3]. Therefore, it should be adequate to interpret 114 115 the data derived and statistics from the study.

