On the day of the formal experiment, participants had breakfast and lunch at 08:00 and 12:00, respectively. The participants arrived at the office at approximately 23:20 for the experiment. A brief explanation was given and the cognitive test was administered at 23:30, which took about 20 minutes to complete, after which the subjects were ready to go to work. At 03:30, according to the randomized results, the subjects were given two pieces of caffeinated chewing gum at an absolute dose of 200 mg (Military Energy Gum®, Ford Gum and Machine Go, Akron, NY, USA) (CAF trial) 146 or two pieces of similar looking and tasting placebo gum that did not contain caffeine (xylitol, lime mint, green; Lotte, Saitama, Japan) (PLA trial). After 10 minutes of 147 148 chewing, cognitive function tests were administered. Finally, the last cognitive function tests were performed after duty at 08:20. All subjects used a dedicated computer with a 149 screen frame rate of at least 240 Hz and a mouse response rate of 1ms. 150 151 To explore the validity of the blinding method, we asked the participants (before and after the test) to identify the supplements they ingested. To do this, the question 152 was as follows: "Which supplement do you think you ingested?" There are three 153 possible answers to this question: (a) caffeine; (b) placebo; and (c) don't know. 154 155 Furthermore, the occurrence of side effects or complications was recorded during the 156 trial.

157 **2.3.2.** Outcome measure

158 2.3.2.1. Cognitive function tests

159 Subjects were sequentially given five tests: Corsi block test, Task-switching 160 paradigm, Stroop Test, Visual search, and Wisconsin Card Sorting Task. All the above 161 cognitive function tests were conducted using Psych/Lab for Windows. Measures used 162 in the literature have satisfactory reliability and validity[27].

163 **2.3.2.1.1.** Corsi block test

164 There will be 9 purple squares in the screen, when the test starts, it will flash a

165 number of them randomly in yellow color (the more the number increases), then you will hear "Go", then you have to click the order of the flashing ones, and then press 166 "DONE" in the lower right corner. The smiley face means correct, the crying face 167 means wrong. The maximum number of correct answers will be displayed at the end of 168 the test, which is mainly to test the ability of situational awareness and working memory. 169 170 The whole process takes about 2 minutes[28-30].

171

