2.3.2.2. Measure Of Sleep

208 Participants wore a wrist ActiGraph (wActiSleep, Pensacola, Florida, United States) on the nondominant hand for 2 sleep periods, including the sleep on off day and 209 the sleep before the first third night duty. The sleep data were obtained from ActiGraph 210 211 monitors and analyzed by ActiLife software version 6 using the Cole-Kripke algorithm, 212 including eight sleep indices (sleep latency, total counts, sleep efficiency, total sleep time [TST], wake after sleep onset [WASO], number of awakenings, length of 213 214 awakenings, time in bed)[39, 40]. Participants also recorded the time they went to bed and woke up to enable coordinate checks with the actigraphic data. Daily sleep quality 215 216 was measured using a question that was chosen because it was easy to conceptualize, 217 simple to understand, and less burdensome for participants. The question asked was: On a scale of 0-10, with 0 being the worst sleep and 10 being the best, rate the quality 218 219 of the previous sleep[41].

Participants self-reported age, marital status, exercise habits, smoking, caffeine and alcohol consumption, and chronic diseases. Height and weight were measured from which body mass index (BMI) was calculated as weight in kilograms divided by the square of height in meters (kg/m2).

224

225 Statistical analysis

226	All data are presented as averages \pm standard deviations. The Shapiro–Wilk test	-	
227	was used to examine the normality of the data. Cognitive performance, accuracy, and	L	
228	hit reaction time were analyzed through a paired sample t test. Effect sizes were	;	
229	calculated using Cohen's D. Tests were performed (t tests or $\chi 2$ tests) to test for	•	
230	differences at baseline between the two groups. A 2 \times 2 mixed-design analysis of		
231	variance with repeated measures was used to examine the effects of the intervention.		
232	The Bang's Blinding Index (BBI) was used to explore the effectiveness of the blinding		
233	whereas the McNemar test was used in the comparison of the incidence of side-effects	•	
234	between the placebo and caffeine conditions. All data were calculated using SPSS		
235	(version 20, Chicago, IL, USA), and the significance level was $\alpha < 0.05$.		
236			
237			
238	1. Prasad, R. V.; Gupta, S. L.; Swaminathan, S., Evaluation of Cognitive and		
239	Psychomotor Functional Changes in Anesthesiology Residents after 12 hours		

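### The baseline significance test does not fit a crossover of the same 14 physicians, and the plan does not say how each night's 23:30 score enters the treatment comparison

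*Combined protocol and SAP*

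**What the plan says.** Section 2.1 sets out a crossover: "physical differences, a crossover trial was conducted with the same group of subjects". Section 2.2 gives the size: "Fourteen healthy male emergency physicians were recruited in this study and". On each experimental night there are three test sessions (section 2.3.1). Before the shift, "A brief explanation was given and the cognitive test was administered at 23:30". After the gum is handed out at 03:30 and chewed for ten minutes, "chewing, cognitive function tests were administered". The final "tests were performed after duty at 08:20".

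The Statistical analysis section makes three relevant statements.
- Baseline: "Tests were performed (t tests or" chi-square tests) were used to look for "differences at baseline between the two groups". It does not define the groups, list the baseline variables, or say whether the t test is paired.
- Outcomes: cognitive performance, accuracy and hit reaction time go to a paired t test, with no baseline term stated.
- Intervention effect: a 2 × 2 mixed-design repeated-measures ANOVA, with no factors or levels named.

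Section 2.1 also says "Randomized groups were created using Microsoft 365-Excel", so the word for groups is used for the randomised allocation as well.

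**The concern.** A comparison of two groups at baseline belongs to a parallel-group trial. Here, if the groups are the two gums, they contain the same people. Age and height cannot differ between them. The 23:30 scores can differ, because the nights are at least four weeks apart, but they come in pairs, and an unpaired test would ignore that. A reassuring non-significant result would then carry little information.

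The 23:30 score also has a better use. It is measured on each night before any gum is given, so it is a legitimate covariate for that night's later scores. Nothing in the plan says whether or how it is used. With 14 participants, night-to-night variation in starting performance may take up a worthwhile share of the error in the CAF–PLA difference. What is at stake is precision and a clear specification, not the validity of the main comparison.

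**Working it through.** **The plan's own figure.** None is given for the baseline comparison, so there is nothing to reproduce.

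**Inputs.** From the documents: n = 14, both gums in each person, tests at 23:30, mid-shift and 08:20. Assumed, because the documents do not give them: the between-night correlation r of a 23:30 score; the correlation rho between the within-person 23:30 difference and the within-person outcome difference; normal data; an equal 7/7 split of sequences.

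**Step 1. Size of the baseline test under each reading.** With SD σ and correlation r, the mean difference between nights has variance 2σ²(1 − r)/n. The unpaired test works as if it were 2σ²/n, so its standard error is too large whenever r > 0. Simulated rejection with no true difference, nominal 5%, n = 14 pairs:

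| r | unpaired t (26 df) | paired t |
|---|---|---|
| 0 | 5.0% | 5% |
| 0.5 | 0.8% | 5% |
| 0.7 | 0.16% | 5% |
| 0.8 | 0.03% | 5% |

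Repeat runs gave 0.81–0.85%, 0.14–0.16% and 0.02–0.03% for the last three unpaired entries. An unpaired t test between two sequence groups of 7 has size 5.0%.

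**Step 2. What the unpaired version would miss.** Take a true night-to-night difference that a paired test detects 80% of the time. The unpaired test detects it 56%, 29% and 12% of the time at r = 0.5, 0.7 and 0.8. For a difference of a full SD, it detects 79%, 83% and 86%.

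**Step 3. Does a stated analysis use the 23:30 score?** The paired t test has no stated baseline term. The ANOVA could have time as a factor with 23:30 as a level, but a two-level factor cannot hold all three sessions. Mixed-design also implies a between-person factor, whereas gum varies within person. The use of the 23:30 score is therefore unspecified, but not excluded.

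**Step 4. Gain or loss from adjustment.** Regress each person's CAF–PLA outcome difference on the CAF–PLA difference at 23:30. Relative to the unadjusted paired difference, the variance of the estimate is multiplied by
- without a period term: (1 − rho²) × (n − 2)/(n − 3) = (1 − rho²) × 12/11
- with a period (sequence) term: (1 − rho²) × (n − 3)/(n − 4) = (1 − rho²) × 11/10

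| rho | 1 − rho² | × 12/11 | × 11/10 |
|---|---|---|---|
| 0 | 1.00 | 1.091 | 1.100 |
| 0.3 | 0.91 | 0.993 | 1.001 |
| 0.5 | 0.75 | 0.818 | 0.825 |
| 0.7 | 0.51 | 0.556 | 0.561 |

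Break-even is at rho = √(1/12) = 0.29 without the period term and √(1/11) = 0.30 with it. Simulation agrees with both columns to within 0.005.

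**Step 5. In terms of power.** Assume a standardised paired difference of 0.8, two-sided 5%, n = 14 and no period term. The unadjusted paired t test has power 0.79. Adjustment gives 0.76, 0.79, 0.86 and 0.95 at rho = 0, 0.3, 0.5 and 0.7. A plain change from 23:30 gives 0.50, 0.65, 0.79 and 0.95, so it is never clearly better than adjustment in this range and is much worse at low rho.

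**The case against.** The strongest reply is that the sentence may describe something harmless. In a crossover it is the sequence that is randomised, section 2.1 uses the same word for the randomised allocation, and the analysis text calls the gums conditions when it compares side effects. A mixed-design ANOVA needs a between-person factor, and sequence is a natural one. On that reading the test has correct size. The authors also clearly recognise pairing, since they name a paired t test and McNemar's test. This stands as far as it goes: the documents do not settle the reading. But the same contrast cuts the other way, because pairing is named elsewhere and not here. A sequence comparison would only ask whether randomisation produced chance differences.

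Three stronger conclusions might be inferred, and the documents support none of them.
- That the baseline test is invalid. This needs both the gum-condition reading and an unpaired test, and even then the error is conservative. The test is also not blind to large differences (Step 2).
- That the 23:30 scores go unused. The ANOVA may include them.
- That leaving out the adjustment biases the result. Chance differences between nights do not bias a randomised paired contrast; they are already in its standard error. Nor does the plan say that the baseline test will be offered as evidence of comparability.

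It is also fair to say that baseline adjustment in a crossover is optional and that its benefit here rests on an unknown correlation.

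**Conclusion.** The point holds as a matter of specification and efficiency. The baseline test is worded for a parallel-group trial and helps the treatment contrast under no reading: it is very conservative if unpaired across gums, and correctly sized but uninformative about that contrast if paired or between sequences. The role of the 23:30 score is left open.

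The unadjusted paired comparison is valid. Adjustment runs from a loss of about 9–10% in variance at rho = 0, through break-even near 0.3, to gains of about 18% at 0.5 and 44% at 0.7. The sizes in Step 1 rest on assumed between-night correlations and normal data, the gains rest on rho, and the period-term column also assumes equal sequences. This is a cheap improvement, not a flaw that undermines the trial.

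**What to change.** 1. Delete the baseline t and chi-square tests. Describe the 14 participants once, by sequence if wanted. If any baseline comparison is kept, define the groups and state the test.
2. For each cognitive score at the mid-shift and 08:20 tests, prespecify the within-person CAF–PLA difference regressed on the within-person CAF–PLA difference in the same test at 23:30, with a sequence term coded +1/−1 to carry the period effect. Do not centre the 23:30 difference at its sample mean: the treatment effect is the intercept at zero baseline difference. An equivalent choice is a mixed model with condition, period, that night's 23:30 score as a deviation from the person's own mean, and a random participant effect.
3. Report the unadjusted paired difference beside the adjusted one.
4. Name the factors and levels of the 2 × 2 ANOVA, or replace it with the model in item 2.

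The cost is a change of wording and some extra output from the software already named, with no new data. The downside of the covariate is one degree of freedom and up to about 10% in variance if the 23:30 difference proves unrelated to the outcome difference. The choice should be fixed before unblinding, not made after seeing which version looks better.

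### The 2 × 2 mixed-design ANOVA assigned to the intervention effect has no named between-subject factor, outcome, test time or rank, although gum and test time are both within-subject in this crossover

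*Combined protocol and SAP*

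**What the plan says.** Section 2.1 (Design) describes a crossover: to remove individual "physical differences, a crossover trial was conducted with the same group of subjects". Section 2.3.1 (Experimental procedure) puts the cognitive battery at 23:30, after ten minutes of chewing from 03:30, and at 08:20. Cognition is the primary outcome and sleep quality the secondary one (section 2.1).

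The Statistical analysis section then gives three instructions:

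- Cognitive performance, accuracy and "hit reaction time were analyzed through a paired sample t test". No test time is given, and it is not said whether the raw score or the change from 23:30 is compared.
- t or χ² tests look for "differences at baseline between the two groups".
- A 2 × 2 mixed-design analysis of "variance with repeated measures was used to examine the effects of the intervention". Its factors, levels, outcome and test time are not stated.

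Neither sequence nor period appears in that section, and nothing says whether the t test or the ANOVA decides.

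**The concern.** A mixed-design ANOVA needs at least one between-subject and one within-subject factor. The two factors that an analyst would reach for here, gum and time, are both within-subject, and time has three levels rather than two. The method given the job of examining the intervention therefore does not match the evident data layout, and the plan does not supply the factor that would make it match.

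Two analysts following the section could fit different models at different test times. One natural choice, gum group × time, uses the wrong error term because it discards the pairing that the crossover was designed to provide. With 14 physicians that choice can settle the result.

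**Working it through.** **Inputs.** From the documents: 14 physicians, two gums, three test times, α = 5%. The documents give no correlation, variance or effect size, so all of those below are assumptions. The plan has no figure for the ANOVA to reproduce. Its only sample-size figure, six subjects at 80% power, comes without an effect size or test. A two-sided paired t test would need a standardised paired difference (dz) of 1.435 to give it.

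**Step 1: count factors and degrees of freedom.**

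| Layout | Between-subject factor | Error df |
|---|---|---|
| Gum (2) × time (3), as the design implies | none | gum 13; gum × time 26 |
| Gum group × time (2), gum taken as between-subject | gum, with 28 records | 28 − 2 = 26 |
| Sequence × gum at one test time | sequence | 14 − 2 = 12 |
| Gum × two sleep occasions | none | 13 |

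Only the third row is truly 2 × 2, mixed and valid. One 2 × 2 model of gum by time also leaves out one of the three test times.

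**Step 2: fix a reference effect.** At n = 14, dz = 0.81 gives noncentrality 0.81 × √14 = 3.03 on 13 df, and hence 80% power for a two-sided paired t test of change from 23:30.

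**Step 3: gum group × time, judged on the interaction.** Let each night's change have variance σ², with correlation ρ between nights. The paired difference has variance 2σ²(1 − ρ), but the unpaired test uses 2σ². Its standard error is too large by 1/√(1 − ρ). By simulation:

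| ρ | SE ratio | Power, unpaired | Null rejection, unpaired |
|---|---|---|---|
| 0 | 1.00 | 83% | 5.0% |
| 0.3 | 1.20 | 71% | 2.2% |
| 0.5 | 1.41 | 56% | 0.8% |

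The paired test has 80% power and 5% null rejection throughout. At ρ = 0 the unpaired test gains slightly from its extra degrees of freedom.

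**Step 4: the same model, judged on the gum main effect.** Use 23:30 and mid-shift, total variance 1, between-physician share s, the rest residual, and an effect at mid-shift only. The mean of two scores, differenced between nights, has variance 1 − s. The unpaired test uses 2[s + (1 − s)/2] = 1 + s. The SE ratio is √[(1 + s)/(1 − s)].

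| s | SE ratio | Power, unpaired | Power, paired |
|---|---|---|---|
| 0.3 | 1.36 | 60% | 80% |
| 0.6 | 2.00 | 20% | 80% |
| 0.8 | 3.00 | 2% | 80% |

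In this set-up ρ = 0, so the interaction loses nothing while the main effect can lose almost everything.

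**Step 5: two unranked tests.** Suppose that both a paired t test on the mid-shift score and a within-subject gum × time test (23:30 v mid-shift) are applied to cognition, and that either may count. Simulated false positives per outcome are 8.4–9.1% over nine assumed variance splits; the three splits of step 4, simulated separately, give 8.3–8.5%. For two independent tests the figure would be 1 − 0.95² = 9.75%. If the t test is itself on change from 23:30, it is the same test as the 2 × 2 within-subject interaction (F = t²), and the figure stays at 5%.

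**Step 6: does period matter to the remedy?** Take seven physicians per sequence (assumed) and let period shift the paired difference by ±0.5 or ±1 of its SD. Power of the plain paired t test falls from 80% to 72% or 48–49%. Sequence × gum stays at 79–80%. With no period shift, moving from 13 to 12 error df costs 80.0% − 79.4% = 0.6 points.

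**The case against.** The strongest defence is that the plan is under-specified rather than wrong, because sequence × gum at one test time is a proper 2 × 2 mixed ANOVA. The text gives this some support. Section 2.1 speaks of randomised groups, and in a crossover order is what gets randomised. It also says that neither the subjects nor the resident "experimenting knew which group the subjects were assigned to or what type of gum", which separates group from gum. Baseline χ² tests on person-level items such as smoking make sense between two order groups but hardly between two gums in the same people. This stands: a reader might infer that the ANOVA cannot be run at all, and the documents do not support that. They equally do not establish sequence × gum, since sequence is never named and section 2.1 also divides the study into a caffeine trial and a placebo trial.

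A second defence is that the 2 × 2 belongs to sleep: two gums by "on the nondominant hand for 2 sleep periods, including the sleep on off day and" a pre-duty sleep. The level count fits, but both factors are again within-subject. In section 2.1 the occasions are "one night on the off day and the last sleep before the first night shift", and that last sleep precedes the gum. It could not serve the Introduction's aim, where sleep monitoring "was performed to observe whether caffeine supplementation affected subsequent sleep". The wording of section 2.3.2.2 leaves the second occasion unclear.

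Third, treating gum as between-subject is mostly conservative, and the paired t test on cognition is valid. Both points stand in general. One exception to the first: with unblocked randomisation, which section 2.1 does not exclude, and an assumed period effect of 1 SD of change, simulated null rejection for the unpaired test was 7.3%.

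Finally, a reader might infer that the plan raises the false-positive rate to 8–9%. It does not say that either test may count as success, nor that cognition enters both. It does not exclude this either.

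**Conclusion.** The point holds and should be fixed. The sentence assigning the intervention effect to a 2 × 2 mixed ANOVA does not match a crossover whose gum and time factors are both within-subject, and it omits the factor, outcome, test time and rank that would make it usable. That rests on the text alone and is secure.

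The size of the harm depends on the reading chosen and on assumed correlations and variances. Under gum group × time the main risk is lost power: from none to 24 points (80% to 56%) for the interaction, and from 20 to 78 points (80% to 60% or 2%) for the main effect. Under sequence × gum there is no such loss. The 8–9% false-positive figure is conditional on an either-test rule and is not a property of the plan as stated.

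**What to change.** Replace the ANOVA sentence with one deciding analysis that keeps gum within-subject and accounts for period. Either of these would do:

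- The CAF − PLA difference in change from 23:30 at one named post-gum time, with a sequence (period) term and a 95% CI. This is the sequence × gum mixed ANOVA on change, with gum tested on F(1,12), so it stays close to what may have been intended.
- A linear mixed model with gum, time, gum × time and period as fixed effects and physician as a random effect, with the deciding contrast named.

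Name the outcome to which it applies. Label the other post-gum time and the remaining paired t tests as supporting. If the two groups in the baseline tests are CAF and PLA, drop those independent-groups tests; if they are sequence groups, say so.

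The cost is some rewording, a different SPSS specification and one degree of freedom for period (13 to 12 in the first option). No new data are needed. The Project summary already reports the sample's age, height and weight. If outcomes had also been seen by then, the revised analysis must be labelled post hoc.
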